5.1.7. Return or destruction of Investigational Medicinal Product

At each study visit, the participant should return all the empty, partially used, or unused blisters as well as the box.

Once the clinical trial is finished, the entire remaining unused IMP, as well as the boxes of used medication (empty or partially used) will be returned for central destruction.

Any return of the remaining IMP will be documented according to the correspondent SOP of the study center.

5.2. Selection of Doses in the Study

Results from the Phase I single and multiple oral doses of vafidemstat (0.2 mg; 0.6 mg; 1.5 mg; 2.5 mg; 4 mg for the single dose study and 0.2 mg; 0.6 mg; 1 mg; 1.5 mg; 2.5 mg and 4 mg for the multiple dose study) in healthy young and elderly volunteers showed a good safety and tolerability profile. Thus, vafidemstat 4.0 mg/day was the MID for a multiple dose regimen as participants who received the active treatment reported a significant decrease (≥50% from baseline) in the platelet count. Considering that the MID was met at this dose, the MTD was 2.5 mg/day based on the guiding principle for dose adjustment, to avoid unnecessary over- or under-exposure to a given active ingredient.

Vafidemstat dose selection was initially based on toxicology, pharmacokinetic and pharmacology non-clinical studies allowing the estimation of the clinically safe and effective dose. In particular, the NOAEL established from short and long-term rat and dog toxicology studies corresponded to human equivalent doses (HED) in the range of 2-4 mg/day, being platelet and neutrophil depletion the most relevant (on-

target) tolerability effects. Additionally, maximum target engagement and signs of therapeutic activity had been observed in non-clinical efficacy models from doses as low as the HED of 0.5 mg/day. Subsequently, appropriate vafidemstat safety and tolerability had also been shown in healthy volunteers in a 5-day treatment Phase I clinical trial and in patients at several long-term (up to 15 months) Phase IIa trials. Doses of 0.6 mg/day and 1.2 mg/day have been used in these Phase II trials. None of these two doses had any clinically relevant hematological impact. Furthermore, in the REIMAGINE Phase IIa clinical study, efficacy in reducing aggression in BPD patients as well as a significant improvement in the overall function was shown with a 1.2 mg/day dose of vafidemstat (see Section 1.4.2). Therefore, is considered appropriate to evaluate this dose of vafidemstat, 1.2 mg/day, in a BPD population.

- **Placebo**

Name: Placebo

Pharmaceutical form: [REDACTED]

Administration route: Oral

Unit Dose: [REDACTED], packed in blisters (blisters of 2 or 5 capsules, 3 blisters in a box)

Manufactured by: [REDACTED]

- **Dose – 1.2 mg**

Name: vafidemstat

Pharmaceutical form: [REDACTED] packed in blisters (blisters of 5 capsules, 3 blisters in a box)

Administration route: Oral

Unit Dose: 1.2 mg

Manufactured by: [REDACTED]

If a participant's medication is lost by breakage or spillage, the PI will retrieve the replacement medications and communicate to the Sponsor. The reason why the replacement medication has been used should be documented on the eCRF "Comments Form".

5.3. Blinding

To guarantee double-blind conditions, vafidemstat and placebo will be presented in identical capsules consisting of special opaque material for clinical studies, and participants will take the same number of capsules daily. The sample labels will have no information that would allow identification of the treatment administered.

The IWRS unblinding procedure is described in the IWRS User Guide.

The study randomization should only be broken for valid medical or safety reasons, for example, a SAE where it is necessary for the PI to know which treatment the participant is receiving to ensure the appropriate SAE treatment. In the event of an emergency, the PI will have to decide on the necessity of unblinding the participant's treatment assignment. The PI will report about this event to the Sponsor as soon as possible. If unblinding occurs, the investigator must record the reason for unblinding, as well as the date and time of the event. Corresponding information will be recorded on the eCRF and will be documented in a note to file which will be filed in the Trial Master File.

5.4. Post-study Access to IMPs

Post-study access to the IMP will not be available.

6. Prior and Concomitant Therapy

Prior medication is defined as medication received prior to first IMP intake. Any medication received at least once after the first IMP intake will be considered as concomitant medication.

All prior medications taken within four weeks prior to screening will be recorded in the eCRF at Visit 1.

Concomitant medication will be recorded in the concomitant medication log/page of the eCRF throughout the study. Prior to initiating a new concomitant medication, participants should check with their study doctor.

Participants will be asked to maintain a stable regimen of background pharmacological therapy, not to initiate any prohibited medications during the trial and to advise their study physician of any medication changes throughout the study.

Psychotherapy treatment should also be registered in the eCRF.

6.1.1. Permitted/Prohibited psychotherapy

Considering that psychotherapy is the standard of care for BPD, all enrolled participants will need to maintain their pre-screening psychotherapy schedule throughout the trial duration. Participants entering the study cannot start any type of psychotherapy within 3 months prior to enrollment or throughout the trial duration.

Specifically, participants receiving psychotherapy before initiating the study need to remain in psychotherapy throughout the trial. However, those participants not receiving psychotherapy before the study should not initiate psychotherapy during the trial. Participants deemed needing immediate or emergent psychotherapy and those initiating psychotherapy during the study will be discontinued from the trial.

6.1.2. Prohibited/Permitted concomitant medications

Prohibited concomitant medications are shown below in [Table 2](#). These concomitant medications are prohibited for the duration of the study. Washout periods prior to Visit 1 (Screening) are described in [Table 2](#). The administration of these medications during the study treatment will lead to withdrawal of the participants from the study (see Section 4.2).

Any concomitant medications for psychiatric comorbidities (as per inclusion/exclusion criteria) are allowed when these medications are used as prescribed (see [Table 3](#)).

Table 2. Prohibited Concomitant Medication

	Washout period before Screening Visit (weeks)
Anticoagulants (e.g.: acenocumarol, warfarin, apixaban, dabigatran and rivaroxaban) - Only 81 mg acetylsalicylic acid is permitted	2
Short and medium half-life oral benzodiazepines are allowed in occasional short-term prescription. Participants should not take these medications within 24 hours before any study visit	8
Z-drugs (i.e.: zaleplon, zolpidem, zopiclone) are allowed in occasional short-term prescription. Participants should not take these medications within 24 hours	2

	Washout period before Screening Visit (weeks)
before any study visit	
Corticosteroids or immunosuppressant (only inhaled or topical suspension are allowed)	2
Typical antipsychotics	5
Long half-life benzodiazepines	8 - 21
Esketamine (in the past 90 days)	2.5
MAO inhibitors	2

Table 3. Allowed Concomitant Medication to be used with caution

UGT Inhibitors (e.g.: adenine, propofol, flunitrazepam, ertugliflozin, ketoconazole, valproic acid, flurbiprofen, silibinin, sodium aurothiomalate, gemfibrozil, deferasirox, probenecid, amitriptyline, indomethacin, ubrogepant)

UGT inducers (e.g.: carbamazepine, phenytoin, phenobarbital, rifampicin, testosterone propionate, lamotrigine, primidone, ethinylestradiol, desogestrel, orthosiphon stamineus)

Antidepressants in stable dose for at least 2 months before the Screening visit is allowed for the treatment of psychiatric comorbidities when these medications are used as prescribed per the inclusion and exclusion criteria*

Atypical antipsychotics in stable dose for at least 2 months before Screening visit is allowed for the treatment of psychiatric comorbidities *

Mood stabilizers in stable dose for at least 2 months before Screening visit is allowed for the treatment of psychiatric comorbidities when these medications are prescribed as per their labelled indications*

Nootropics (e.g.: racetams, amphetamines, methylphenidate, levodopa, atomoxetine, preparations containing Gingko biloba) in stable dose for at least 2 months before Screening are allowed for the treatment of psychiatric comorbidities when these medications are prescribed as per their labelled indications*

Centrally active anti-hypertensive drugs, such as clonidine, a-methyldopa, and guanfacine, as well as guanethidine, in stable dose for at least 2 months before Screening are allowed but should be used with caution.

Medications which may have an impact on blood count changes (e.g.: heparin, quinine, quinidine, penicillin, sulphonamides, NSAIDs, anticonvulsants, antirheumatics, oral antidiabetics, gold salts, diuretics rifampicin, ranitidine). Drug-Drug Interactions (DDI) interactions should be reviewed in the label of the concomitant medication.

Platelet aggregation inhibitors (e.g.: COX-2 inhibitors, ADP receptor inhibitors, thromboxane inhibitors). Drug-Drug Interactions (DDI) interactions should be reviewed in the label of the concomitant medication.

* Always as per inclusion/exclusion criteria

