8. Clinically significant, advanced or unstable disease that is likely to result in rapid deterioration of the participant's condition or affect their safety during the study, including but not limited to:
 - a. Seizure disorders, excluding febrile seizures of childhood
 - b. Respiratory insufficiency, the status must be determined as usual clinical practice
 - c. Hepatic impairment (serum values of total bilirubin value, alanine aminotransferase

- [ALT], aspartate aminotransferase [AST] and gamma-glutamyltransferase [GGT] 1.5 x upper limit of normal [ULN])
- d. Renal insufficiency (serum creatinine >2mg/dl)
 - e. Heart disease (myocardial infarction, unstable angina, heart failure, cardiomyopathy within 6 months before Screening visit)
 - f. Hypertension treatment with more than 2 drugs
 - g. Atrioventricular block (type II/Mobitz II and type III), congenital long QT syndrome, sinus node dysfunction or prolonged QTcF-interval (males >450 msec and females >470 msec)
 - h. Uncontrolled diabetes (Hb1Ac >7.5)
 - i. Hematological disorders
 - j. Platelets <130,000/mm³ and/or neutrophils <1,800/mm³
 - k. Malignant tumors within the last 5 years other than basal cell or Stage 1 squamous cell carcinoma of the skin
9. Positive results for tuberculosis (the status must be determined as usual clinical practice, i.e., by medical history, signs and symptoms), Human Immunodeficiency Virus (HIV), Hepatitis C or Hepatitis B (Hepatitis B surface Antigen [HbsAg]) serology obtained at the Screening Visit.
10. Uncontrolled hypo- or hyperthyroidism at Screening Visit, based on laboratory parameters.
11. Clinically significant infection within the previous 30-days (e.g., persistent or acute infection such as a urinary tract infection or upper respiratory infection).
12. Chronic drug intake of:
- a) Anticoagulants (only 81 mg/day acetylsalicylic acid is permitted).
 - b) Short and medium half-life oral benzodiazepines are allowed in occasional short-term prescription use. Participants should not take these medications within 24 hours before any study visit. Long half-life benzodiazepines are not allowed.
 - c) Z-drugs – i.e.: zaleplon, zolpidem, zopiclone – are allowed in occasional short-term prescription use. Participants should not take these medications within 24 hours before any study visit.
 - d) Corticosteroids or immunosuppressant (only inhaled or topical suspension are allowed).
 - e) Myelosuppressive treatments such as chemotherapy and radiation.

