4.10 Concomitant Medication

Medication start and stop dates will be compared to the date of first dose of study medication to allow medications to be classified as either Prior only, both Prior and Concomitant, or Concomitant only. Medications starting after the completion/withdrawal date will be listed but will not be classified or summarized.

Medications that start and stop prior to the date of first dose of study medication will be classified as Prior only. If a medication starts before the date of first dose of study medication and is either ongoing or stops on or after the date of first dose of study medication, then the medication will be classified as both Prior and Concomitant. Medications will be classified as Concomitant only if they have a start date on or after the date of first dose of study medication.

If medication start and/or stop dates are missing or partial, the dates will be compared as far as possible with the date of first dose of study medication. Medications will be assumed to be Concomitant only, unless there is clear evidence (through comparison of partial dates) to suggest that the medication started prior to the first dose of study medication. If there is clear evidence to

suggest that the medication started prior to the first dose of study medication, the medication will be assumed to be both Prior and Concomitant, unless there is clear evidence to suggest that the medication stopped prior to the first dose of study medication. If there is clear evidence to suggest that the medication stopped prior to the first dose of study medication, the medication will be assumed to be Prior only.

Prior and Concomitant medications will be coded according to WHO Drug Dictionary.

Summaries of both Prior and Concomitant medication will be provided for the SAF analysis set by actual treatment arm, displaying the number of percentage of subjects being treated with each type of medication/therapy classified according to ATC level 2 (therapeutic main group) and ATC level 3 (pharmacological subgroup). An additional summary will be created for only prohibited medication (as per Table 2 of the CSP).

A similar summary will be provided for Prior medication.

Medication will also be listed, including classifications, start and end dates, indication, frequency and dose as well as other available variables.

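### Protocol 6.1.2 and Table 2 both prohibit and allow occasional use of shorter-acting benzodiazepines and Z-drugs, the consequence of use is stated in three ways, and the esketamine row contradicts itself

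*Protocol*

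**What the plan says.** Protocol 6.1.2 introduces Table 2 with two rules that carry no exception. The first is "These concomitant medications are prohibited for the duration of the study". The second is "The administration of these medications during the study treatment will lead to withdrawal of the participants from the study", followed by a pointer to Section 4.2. The table's only numeric column is headed "Washout period before Screening Visit (weeks".

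Three rows matter here:

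- Benzodiazepines: "Short and medium half-life oral benzodiazepines are allowed in occasional short-term prescription", with none to be taken in the 24 hours before a visit. Washout column: 8.
- Z-drugs: "Z-drugs (i.e.: zaleplon, zolpidem, zopiclone) are allowed in occasional short-term prescription", with the same 24-hour limit. Washout column: 2.
- Esketamine: the row label reads "Esketamine (in the past 90 days". Washout column: 2.5.

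In Protocol 4.1.2, exclusions 12b and 12c say that both classes "are allowed in occasional short-term prescription use". They repeat the 24-hour limit and give no washout. The stem of exclusion 12 speaks of chronic intake. Exclusion 13 bars esketamine in the 90 days before Screening.

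Two other protocol sections deal with the consequence. Section 4.2 lists starting a prohibited medication, citing Table 2, among possible reasons for withdrawal. Section 10.9 counts starting a prohibited medication as a major deviation, without citing Table 2, and lets the sponsor decide whether a major deviation ends participation.

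SAP 4.10 takes its list directly from the table: "An additional summary will be created for only prohibited medication (as per Table 2 of the CSP".

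**The concern.** A site reading the text of 6.1.2 literally would screen out a candidate who took a short-acting benzodiazepine five weeks before Screening, and would withdraw a participant who took one between visits. A site reading exclusion 12b, or the wording of the Table 2 row, would accept both. The protocol supports either action for the same dose, at approximately 20 sites in Europe and the US.

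Three things are at stake. Participants and sites lack a clear rule. Some withdrawals or screen failures may be avoidable. And the tabulation of prohibited medication may mix permitted users with real violators.

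There is also a route to the primary analysis. SAP 4.6 keeps data after concurrent treatments under a treatment policy strategy, but uses a hypothetical strategy for early study termination. The same occasional dose would leave later visits observed at one site and missing at another.

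**Working it through.** This is a consistency check. The only arithmetic is unit conversion.

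**1. Check the unit of the washout column.** Exclusion 12g bars MAO inhibitors for 14 days before Screening, and Table 2 gives 2. Since 14 / 7 = 2.0, the column is in weeks, as its heading says.

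**2. Benzodiazepines and Z-drugs, side by side.**

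| Point | 6.1.2 text and washout column | Table 2 row wording and exclusions 12b, 12c |
|---|---|---|
| Status | Prohibited throughout | Occasional short-term use allowed |
| Window, benzodiazepines | 8 weeks before Screening = 8 × 7 × 24 = 1,344 h | 24 h before any study visit |
| Window, Z-drugs | 2 weeks before Screening = 2 × 7 × 24 = 336 h | 24 h before any study visit |
| Use on treatment | Leads to withdrawal | Permitted outside the 24 h |

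Screening is itself a study visit, so both windows apply at that point. They differ by 1,344 / 24 = 56-fold for benzodiazepines and 336 / 24 = 14-fold for Z-drugs.

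**3. The stated consequence of use.**

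- 6.1.2: withdrawal follows.
- 4.2, to which 6.1.2 refers: a possible reason for withdrawal.
- 10.9: a major deviation, with withdrawal decided by the sponsor.

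**4. Esketamine.**

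- Row label and exclusion 13: 90 days, or 90 / 7 = 12.9 weeks.
- Washout column: 2.5 weeks, or 2.5 × 7 = 17.5 days.
- Ratio: 90 / 17.5 = 5.1.
- Reading 2.5 as months does not resolve it: 2.5 × 30.417 = 76 days, which is not 90.

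A person whose last dose was 18 to 90 days before Screening meets the washout column and fails exclusion 13. Protocol 4.1 requires that no exclusion criterion be met, so that person is not eligible. The 2.5 conflicts with its own row label but does not open a second way into the trial.

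**5. Where the conflict reaches the analysis.**

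- SAP 4.10 defines prohibited medication by Table 2. Programmed by drug class, that summary counts every benzodiazepine and Z-drug user, including those whom 12b and 12c permit.
- Major deviations remove participants from the per-protocol set (Protocol 9.2, SAP 4.5). Section 10.9 depends on what counts as prohibited, which is the unresolved question.
- The full analysis set is all randomized participants (SAP 4.5), so its membership does not depend on this.

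**The case against.** The strongest reply is that these rows are a class restriction with an exception. Other Table 2 rows have that form: anticoagulants with low-dose aspirin excepted, corticosteroids with inhaled or topical forms excepted. Exclusion 12 is about chronic intake. A 24-hour limit before any visit has meaning during the study only if some use is allowed. The protocol's change history links the 8-week figure to possible benzodiazepine addiction, which suggests that sustained use was the target.

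This makes the likely intent easier to guess, but it does not repair the text. Neither 6.1.2 nor Table 2 limits its rules to chronic use, and the washouts and the withdrawal sentence carry no exception for occasional use. In the aspirin and steroid rows the exception is a different drug, dose or route. Here the same oral drug is on both sides of the line, separated only by the undefined word occasional.

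Other parts of the reply stand:

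- **Central control.** The sponsor has the final say on participation after medical monitor review (Protocol 4.1). SAP 4.4.2 and 4.5 settle deviations and analysis sets at a blinded data review. Sites therefore do not decide per-protocol membership, and SAP 4.5 uses that set for descriptive purposes only.
- **Withdrawal is not uniformly mandatory.** Sections 4.2 and 10.9 soften the sentence in 6.1.2. A reader might infer a fixed rule of mandatory withdrawal; the protocol read as a whole does not support that.
- **Esketamine.** A reader might infer two competing exclusion windows. There is one exclusion criterion and one table entry that conflicts with it.

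**Conclusion.** The inconsistency is real and lies in the current text. Table 2, read with 6.1.2, gives short and medium half-life benzodiazepines and Z-drugs two statuses and two windows. The consequence of use is stated in three ways. The esketamine row disagrees with itself by a factor of 5.1, without effect on who may enter as long as exclusion 13 is applied. The direct statistical effect is on the SAP 4.10 summary and on how consistently deviations are coded.

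A reader might go further and infer a loss of power. Suppose 5 to 15% of the 150 planned completers were withdrawn for occasional use. That leaves about 143 to 128 completers, or 71 to 64 per arm. With power = Φ(0.51 × √(n/2) − 2.241), 75, 71 and 64 per arm give about 81%, 79% and 74%. The documents do not support this as a finding, for four reasons:

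- The 5 to 15% is an assumption, as no usage rate is given.
- It requires every occasional user to be withdrawn, whereas the problem is that handling may differ.
- It adds these losses to a 20% dropout allowance that is not limited by cause.
- It treats withdrawn participants as contributing nothing, although they stay in the full analysis set and their earlier visits enter the mixed model.

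The effect on power therefore cannot be quantified. The case for correction rests on the conflicting instructions, not on a power figure.

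**What to change.** Reconcile Protocol 6.1.2, Table 2, 4.2, 10.9 and exclusions 12b, 12c and 13 (with the synopsis copy of the criteria) so that each drug class has:

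- one status;
- one window before Screening and before visits, with the esketamine label and column in agreement;
- one stated consequence of use on treatment.

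If the text keeps a distinction between occasional and other use, say how sites are to tell them apart. Which status, window and consequence apply is a clinical decision for the sponsor; this review takes no position on it.

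Then point SAP 4.10 to the reconciled list and state whether permitted occasional use is excluded from the prohibited-medication summary or shown separately. Use the same list in the Protocol Deviation Specification, and settle the coding before unblinding.

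The cost is a protocol clarification or amendment and a short SAP edit. It adds no procedures and changes neither the sample size nor the primary model.

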7. STUDY ASSESSMENTS

7.1. Diagnostic Assessment

7.1.1. Mini-International Neuropsychiatric Interview (MINI)

The Mini-International Neuropsychiatric Interview (MINI) is a clinician-reported outcome measure administered as a structured diagnostic interview. The MINI was developed to enable the use of a brief structured interview for accurate diagnosis in multicenter trials and epidemiological studies (Sheehan *et al.*, 1998). The MINI has multiple modules and can be administered in its entirety or with a subset of the modules. Within each module there are decision trees which allow for screening questions to be asked to determine whether the entire module needs to be assessed. The MINI is designed to be administered by experienced clinicians with the capability to make the clinical judgments necessary to come to an accurate diagnostic profile.

